11.9. Sample Size Determination

In order to determine the sample size, the following assumptions were made:

- *Event rate*: Based on published literature and results from the ENGAGE AF-TIMI 48 study, it is assumed that the event rate of the primary efficacy endpoint of NACE in AF-subjects with TAVI treated with VKA would be 14%/year.
- *Noninferiority margin*: No data were available for placebo-controlled studies in this subject population. The Executive Committee reviewed all available data including practice changes observed in other areas of cardiology on the basis of clinical trials and the level of statistical certainty they had achieved. Then it made the judgment that a noninferiority margin for hazard ratio 1.38 would be accepted by the medical community for a practice change given the fact that other trials have already supported the use of Edoxaban in subjects warranting anticoagulation and its related regulatory approval for human use in the participating countries.
- *Significance level for statistical testing*: 0.05.
- *Observed hazard ratio*: 0.95.

With the above assumptions, to demonstrate noninferiority with 80% of power, the study needs to collect at least 320 NACE across the combined study arms. With an anticipated median follow-up time of two years and an annual event rate of 14%, a total of approximately 1400 subjects need to be randomized.

The sample size is event driven. The sample size or the duration of follow-up may require adjustment based on the actual versus anticipated primary endpoint event and drop-out rates.

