- *Noninferiority margin:* No data were available for placebo-controlled studies in this subject population. The Executive Committee reviewed all available data including practice changes observed in other areas of cardiology on the basis of clinical studies and the level of statistical certainty they had achieved. Then it made the judgment that a noninferiority margin for hazard ratio 1.38 would be accepted by the medical community for a practice change given the fact that other studies have already supported the use of Edoxaban in subjects warranting anticoagulation and given its related regulatory approval for human use in the participating countries.
- *Significance level for statistical testing:* 0.05.
- *Observed hazard ratio:* 0.95.

With the above assumptions, to demonstrate noninferiority with 80% of power, the study needs to collect at least

320 NACE across the combined study arms. With an anticipated median follow-up time of two years and an annual event rate of 14%, a total of approximately 1400 subjects need to be randomized.

The sample size is event driven. The sample size or the duration of follow-up may require adjustment based on the actual vs. anticipated primary endpoint event and drop-out rates.

Subject Eligibility Criteria: Inclusion criteria

Subjects must satisfy all of the following criteria to be included in the study:

1. Successful TAVI via transvascular access routes such as femoral, carotid, axillary, and subclavian arteries. Other access routes need prior approval per majority vote from 3 members of the Executive Committee (both Global Lead Investigators and the Daiichi Sankyo Medical Lead or his/her designee). Success is defined as:
 - a. Correct positioning of a single prosthetic heart valve into the proper anatomical location
 - b. Presence of all 3 conditions post TAVI
 - i. Mean aortic valve gradient <20 mm Hg
 - ii. Peak transvalvular velocity <3.0 m/s
 - iii. Aortic valve regurgitation of 2 or less
 - c. No clinically overt stroke
 - d. No uncontrolled bleeding at time of randomization
 2. Indication for chronic OAC
 - a. Documented pre-existing AF
 - b. New onset AF (e.g., > 30 seconds documented by ECG)
 3. Provision of signed informed consent
 4. Age \geq 18 years
-

Exclusion criteria**Bleeding risks or systemic conditions**

1. Conditions with a high risk of bleeding

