Hypothesis	Endpoint	Primary Analysis Set	Primary Analysis Period
(1)	NACE	ITT	Overall study period
(2)	Major bleeding (ISTH def)	ITT	Overall study period
(3)	Major bleeding (ISTH def)	ITT	Overall study period
(4)	NACE	ITT	Overall study period

To control the type-I error rate, these four hypotheses will be tested in a hierarchical manner:

- Step (1): The Edoxaban-based regimen will be considered noninferior to the VKA-based regimen with regards to NACE, if the upper boundary of the two-sided 95% CI for hazard ratio (HR) falls below 1.38. If it is significant, then go to Step (2), otherwise stop here.
- Step (2): The Edoxaban-based regimen will be considered noninferior to the VKA-based regimen with regards to major bleeding (ISTH def.), if the upper boundary of the two-sided 95% confidence interval (CI) for HR falls below 1.38. If it is significant, then go to Step (3), otherwise stop here.
- Step (3): The Edoxaban-based regimen will be considered superior to the VKA-based regimen with regards to major bleeding (ISTH def.), if the upper boundary of the two-sided 95% CI for HR falls below 1.00. If it is significant, then go to Step (4), otherwise stop here.
- Step (4): The Edoxaban-based regimen will be considered superior to the VKA-based regimen with regards to NACE, if the upper boundary of the two-sided 95% CI for HR falls below 1.00.

For each of the primary and secondary adjudicated endpoints, appropriate summary statistics (e.g., event rate) including 95% CI will be provided.

For each of the adjudicated endpoints, the time from reference date to the first occurrence of an event (based on CEC adjudication), is analyzed using a Cox proportional hazard model with treatment regimen as a factor and all the stratification factors from the randomization (IXRS) as covariates, (dose adjustment [yes, no], to provide point estimates and 95% CI for the HR). Depending on the analysis period used in the statistical analysis, subjects without an occurrence of an event will be censored at the last date of the analysis period or at the last date of known outcomes status. The latter is determined an individual basis for subjects with incomplete follow-up.

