2.2. Study Hypothesis

There are 4 primary hypotheses that will be tested in hierarchical order:

- Hypothesis (1):
 - The Edoxaban-based regimen is noninferior to the VKA-based regimen with regards to NACE.
- Hypothesis (2):
 - The Edoxaban-based regimen is noninferior to the VKA-based regimen with regards to major bleeding (ISTH definition).
- Hypothesis (3):
 - The Edoxaban-based regimen is superior to the VKA-based regimen with regards to major bleeding (ISTH definition).
- Hypothesis (4):
 - The Edoxaban-based regimen is superior to the VKA-based regimen with regards to NACE.

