5.1.2. Method of Treatment Allocation

Prior to randomization of a subject, all eligibility criteria must be met and a signed informed consent obtained.

Enrollment and randomization must occur between the evening of the day of TAVI and 5* days, i.e., until 23:59 of the 5th* day provided that the TAVI procedure has been judged as successful (See inclusion criteria #1 for definition of successful TAVI) and the subject is qualified based on all the protocol defined inclusion/exclusion criteria. All sites will be required to maintain a record of all subjects screened for the trial. The reason for screen failure must be documented in the subject's records. Subjects must be randomized without delay and administered their first dose of study medication within 24 hours post randomization; however, NO EARLIER than the morning after successful TAVI. Randomization will be performed using the IXRS system for subjects meeting all eligibility criteria. The directions on how to use the system will be provided in the IXRS Quick Reference Manual. The randomization scheme will be securely stored at the statistical department of the database management center.

*If subject is waiting on a decision on pacemaker surgery, then can extend to 7 (7th) days

Based on this information, the system will assign a unique subject identification number and treatment for that subject. Trial randomization will not be blinded and once subject is assigned to a treatment arm, no treatment cross-over is permitted. Subjects will be randomly assigned in a 1:1 ratio to receive Edoxaban or VKA. The Investigator will pre-declare the type (if any) P2Y₁₂ antagonist or ASA treatment and its projected last dose prior to the randomization (pre-declaration, via the IXRS).

The Investigator's knowledge of the treatment must not influence the decision to enroll a particular subject or affect the order in which subjects are enrolled.

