11.4.1. Analysis of the primary endpoint(s)

The primary efficacy endpoint is *NACE*, i.e., the composite of all-cause death, MI, ischemic stroke, SEE, valve thrombosis, and major bleeding (ISTH definition).

The primary safety endpoint is *major bleeding (ISTH definition)*.

There are 4 primary hypotheses that will be tested in hierarchical order:

- Hypothesis (1):
 - The Edoxaban-based regimen is noninferior to the VKA-based regimen with regards to NACE.
- Hypothesis (2):
 - The Edoxaban-based regimen is noninferior to the VKA-based regimen with regards to major bleeding (ISTH definition).
- Hypothesis (3):
 - The Edoxaban-based regimen is superior to the VKA-based regimen with regards to major bleeding (ISTH definition).
- Hypothesis (4):
 - The Edoxaban-based regimen is superior to the VKA-based regimen with regards to NACE.

The analysis set and analysis periods to be used for the main analysis related to these four hypotheses are presented below:

Table 11.1: Statistical Analysis Hierarchy for Primary Parameters

Hypothesis	Endpoint	Primary Analysis Set	Primary Analysis Period
(1)	NACE	ITT	Overall study period
(2)	Major bleeding (ISTH def)	ITT	Overall study period
(3)	Major bleeding (ISTH def)	ITT	Overall study period
(4)	NACE	ITT	Overall study period

To control the type-I error rate, these four hypotheses will be tested in a hierarchical manner:

- Step (1): The Edoxaban-based regimen will be considered noninferior to the VKA-based regimen with regards to NACE, if the upper boundary of the two-sided 95% CI for hazard ratio (HR) falls below 1.38. If it is significant, then go to Step (2), otherwise stop here.
- Step (2): The Edoxaban-based regimen will be considered noninferior to the VKA-based regimen with regards to major bleeding (ISTH def.), if the upper boundary of the two-sided 95% CI for HR falls below 1.38. If it is significant, then go to Step (3), otherwise stop here.
- Step (3): The Edoxaban-based regimen will be considered superior to the VKA-based regimen with regards to major bleeding (ISTH def.), if the upper boundary of the two-sided 95% CI for HR falls below 1.00. If it is significant, then go to Step (4), otherwise stop here.
- Step (4): The Edoxaban-based regimen will be considered superior to the VKA-based regimen with regards to NACE, if the upper boundary of the two-sided 95% CI for HR falls below 1.00.

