11.7. Interim Analyses

Not applicable.

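### The stated 80% power does not follow from the stated inputs: 80% needs about 226 NACE, and 320 NACE give about 92%

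*Combined protocol and SAP*

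**What the plan says.** Section 11.9 (Sample Size Determination) lists a noninferiority margin of 1.38, a hazard ratio of 0.95 and, under "Significance level for statistical testing", the value 0.05 without saying whether it is one- or two-sided. From these it states that "to demonstrate noninferiority with 80% of power, the study needs to collect at least 320 NACE across the combined study arms". The synopsis, under Planned Sample Size, makes the same derivation: "With the above assumptions, to demonstrate noninferiority with 80% of power, the study needs to collect at least" 320.

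The sidedness is settled elsewhere. Step (1) of the hierarchy, in the synopsis and in Section 11.4.1, declares noninferiority for NACE "if the upper boundary of the two-sided 95% CI for hazard ratio (HR) falls below 1.38". Section 5.1.2 fixes the allocation: "Subjects will be randomly assigned in a 1:1 ratio to receive Edoxaban or VKA". Section 11.7 (Interim Analyses) reads "Not applicable". Multiplicity is handled by order of testing, not by dividing alpha: "To control the type-I error rate, these four hypotheses will be tested in a hierarchical manner", with a two-sided 95% interval at each of the four steps.

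**The concern.** The 320 events are presented as a consequence of the listed assumptions, so a reader should be able to reproduce them. A margin of 1.38 against an assumed hazard ratio of 0.95 is a wide gap on the log scale, and 320 events looks too many for 80% power.

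Two things are at stake. First, the stated power for the first primary hypothesis may be wrong. Section 11.9 also allows the sample size or follow-up to be adjusted later, which needs a correct link between events and power. Second, if 320 came from an input that is not listed, the trial may have been sized for a different rule from the one that will be applied.

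**Working it through.** **Inputs.** Margin M = 1.38, planning hazard ratio 0.95, level 0.05, power 80% and 320 events (Section 11.9); two-sided 95% interval (Section 11.4.1), so one-sided 0.025 and z = 1.960; 1:1 allocation (Section 5.1.2). For 80% power z = 0.842. The 14% annual rate and the two-year follow-up determine the number of subjects, not the number of events required.

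**Attempt to reproduce 320.** Schoenfeld's formula with 1:1 allocation is D = 4(z_a + z_b)² / [ln(M/HR)]².

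- ln(1.38/0.95) = 0.3734; squared, 0.1394.
- 4 × (1.960 + 0.842)² = 31.40.
- D = 31.40 / 0.1394 = 225.2, so 226 events.
- Freedman's formula, (z_a + z_b)² × [(1 + r)/(1 − r)]² with r = 0.95/1.38 = 0.688, gives 230.5, so 231 events.
- Reading 0.05 as one-sided (z = 1.645) gives 177.4, so 178 events, further from 320.
- 90% power with the two-sided interval gives 301.5, so 302 events.

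The stated figure is not reproduced. It is 42% above 226 (320/226 = 1.42).

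**Power at 320 events.** Power = Φ(ln(1.38/HR) × √320/2 − 1.960). At HR 0.95 this is Φ(0.3734 × 8.944 − 1.960) = Φ(1.380) = 91.6%.

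| True HR | Power at 320 NACE |
|---|---|
| 0.90 | 96.9% |
| 0.95 | 91.6% |
| 1.00 | 82.1% |
| 1.05 | 68.6% |
| 1.10 | 52.7% |

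Freedman's version gives 91.0% at 0.95. A simulation of an event-driven trial (exponential times, 4000 runs, two-year uniform accrual assumed) gave about 90.6% at 320 events and 78.5% at 226, in line with the formulas.

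**Literal reading of the planning value.** The plan labels 0.95 as an observed hazard ratio. If it were the estimate, the upper limit at 320 events would be 0.95 × exp(1.960 × 2/√320) = 1.18, far below 1.38. That does not explain 320 either.

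**Single changes that return about 320 events at 80% power, other inputs as stated.**

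| Change | Events |
|---|---|
| Two-sided alpha 0.0125 (= 0.05/4) | 319.95 |
| Margin 1.30 | 319.1 |
| True HR 1.009 | 320.2 |

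Alpha of 0.05/2 gives 272.7 and 0.05/3 gives 300.4, so those do not match. The plan has four primary hypotheses (Section 2.2: "There are 4 primary hypotheses that will be tested in hierarchical order"), but nothing says alpha was divided by four. All three matches were found by solving backwards.

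**Why the cause matters.** The largest observed hazard ratio that passes at 320 events is M × exp(−2z_a/√320):

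- margin 1.38, 95% interval: 1.108
- margin 1.38, 98.75% interval: 1.044
- margin 1.30, 95% interval: 1.044

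**The case against.** The strongest reply is that nothing is harmed. More events than needed still secure at least 80% power, and the events, subjects and decision rule all stay as they are. On that view this is a loose sentence. The possible causes are also conjecture: 1.38 and the two-sided 95% interval are used consistently, and fixed-sequence testing needs no division of alpha. Ordinary explanations that leave the rule untouched exist too. A true hazard ratio of 1.00 needs 303 events (308 by Freedman), which an assumed 5% loss would raise to 303/0.95 = 319. And 80% might be a slip for 90%, which needs 302 (309 by Freedman).

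Much of this stands. The error is conservative, and no cause can be asserted from the documents. But the benign explanations also rest on inputs that are not stated. Hazard ratio 1.00 and 90% power both fall short of 320 without a further allowance. Section 11.9 gives no drop-out rate, and such an allowance would ordinarily inflate subjects, not required events. Raising 226 to about 320 in that way would take a loss of roughly 29% (1 − 226/320). None of this makes the sentence correct as written.

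**Conclusion.** The concern holds. With margin 1.38, hazard ratio 0.95, a two-sided 95% interval and 1:1 allocation, 80% power needs about 226 NACE (231 by Freedman). The planned 320 give about 92%, so the stated power is about 12 percentage points too low under the rule that will be applied. The result rests on the standard large-sample approximation under proportional hazards, and the choice of formula moves it by less than one point.

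The trial is not underpowered on its own assumptions. At a true hazard ratio of 1.00 power is still about 82%, but it falls to about 69% at 1.05. The source of 320 is unknown. It needs to be found because two candidates, a margin near 1.30 or a two-sided alpha of 0.0125, would mean sizing for a stricter rule than Section 11.4.1 states. The arithmetic is certain; those candidates are inference only. This should be fixed, but it does not threaten the design.

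**What to change.** First check the source calculation for the 320 events.

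- If it used the margin and level in Section 11.4.1, with a different true hazard ratio or power, or an allowance, state that input.
- If it used a different margin or alpha, do not insert that value into Section 11.9 alone. Reconcile it with Step (1) in the synopsis and in Section 11.4.1.

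In every case report power under the rule that will be applied. With 320 events and the present rule kept, the power sentence in Section 11.9 and in the synopsis can be replaced by: *With 320 NACE, a margin of 1.38 and a two-sided 95% confidence interval, power is about 92% if the true hazard ratio is 0.95 and about 82% if it is 1.00.* In the same list, relabel the planning value as the assumed true hazard ratio, and say that 0.05 is two-sided.

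The cost is one check and a few words in two places. Events, subjects and decision rule do not change, unless the check shows that another margin or alpha was intended.

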11.10. Statistical Process

The statistical analysis will be performed by the assigned CRO under the guidance of the Daiichi Sankyo study biostatistician.

A Statistical Analysis Plan will be written providing all the details on the statistical methods and definitions for the analysis of the efficacy and safety data, as well as describing the approaches to be taken for summarizing other clinical study information such as, but not limited to, subject disposition, demographic and baseline characteristics, study drug exposure, and prior and concomitant medications.

To preserve the integrity of the statistical analysis and clinical study conclusions, the SAP will be finalized prior to database lock.

All statistical analyses will be performed using SAS[®] Version 9.3 or higher (SAS Institute, Cary, NC 27513).

12. DATA INTEGRITY AND QUALITY ASSURANCE

The Investigator/investigational site will permit study-related monitoring, audits, IRB/EtC review and regulatory inspections by providing direct access to source data/documents. Direct access includes permission to examine, analyze, verify and reproduce any records and reports that are important to the evaluation of a clinical study. Furthermore, the Investigator/investigational site will supply the CEC with whatever information that is requested such that the CEC will be able to perform their adjudication duties.

12.1. Monitoring and Inspections

The monitor and regulatory authority inspectors are responsible for contacting and visiting the Investigator for the purpose of inspecting the facilities and, upon request, inspecting the various records of the study (e.g., eCRFs, source data, and other pertinent documents).

The monitor is responsible for visiting site(s) at regular intervals (as detailed in the monitoring plan) depending upon the site enrollment and monitoring needs of the site, throughout the study to verify adherence to the protocol; completeness, accuracy, and consistency of the data; and adherence to ICH Good Clinical Practice (GCP) and local regulations on the conduct of clinical research. The monitor is responsible for inspecting the eCRFs and ensuring completeness of the study essential documents. The monitor should have access to subject medical records and other study-related records needed to verify the entries on the eCRFs. Source document verification procedure and process is addressed in the study monitoring plan.

The monitor will communicate deviations from the protocol, SOPs, GCP and applicable regulations to the Investigator and will ensure that appropriate action designed to prevent recurrence of the detected deviations is taken and documented.

The Investigator agrees to cooperate with the monitor to ensure that any problems detected in the course of these monitoring visits are addressed and documented.

In accordance with ICH GCP and the Sponsor's audit plans, this study may be selected for audit by representatives from the Sponsor. Inspection of site facilities (e.g., pharmacy, drug storage areas, laboratories, etc.) and review of study related records will occur in order to evaluate the study conduct and compliance with the protocol, ICH GCP, and applicable regulatory requirements.

12.2. Data Collection

This study employs electronic data capture. The eCRF should be kept current to enable the monitor to review the subject's status throughout the course of the study. The eCRF will be completed, reviewed, and electronically signed by the Investigator. Guidelines will be provided to facilitate data entry in the electronic data capture modules.

All written information, study notes, and other material to be used by subjects and investigative staff must use vocabulary and language that are clearly understood as source documentation.

12.3. Data Management

All data management related tasks, responsibilities, and processes are noted in the data management plan for the study.

Each subject will be identified in the database by a unique subject identifier as defined by the Sponsor.

To ensure the quality of clinical data across all subjects and study centers, a Clinical Data Management review will be performed on subject data according to specifications given by the Sponsor or designee(s). Data will be vetted both electronically and manually for CRFs and the data will be electronically vetted by programmed data rules within the application. Queries generated by rules and raised by reviewers will be generated within the electronic data capture application. During this review, subject data will be checked for consistency, completeness and any apparent discrepancies. In addition, the data will be reviewed for adherence to the protocol and GCP. To resolve any questions arising from the Clinical Data Management review process, eCRF queries will be raised and resolved within the electronic data capture application.

Data received from external sources such as laboratories and IXRS will be reconciled to the clinical database.

Serious Adverse Events in the clinical database will be reconciled with the safety database.

All medical history entries (except terms pre-specified on the eCRF) and AEs will be coded using MedDRA. All prior and concomitant medications will be coded using World Health Organization (WHO) Drug Dictionary.

